### **7.8.1 Biomarkers Assessed by Flow Cytometry**

Summary statistics for activated flow cytometry (e.g., Immunophenotyping/Tetramer) variables and their corresponding changes from baseline will be tabulated by planned timepoints. The time course of these biomarker measures will be investigated graphically (e.g., individual plots of change/percent change from baseline vs. time). If there is any indication of exposure-response relationship, further analyses may be performed to characterize the relationship by fitting appropriate models (e.g., e-max model).

Any potential relationships between the biomarker levels or changes in biomarker levels and clinical outcomes such as tumor response, PFS, and adverse event incidence may be explored using logistic (or Cox) regression, if sufficient samples are collected.

### **7.8.2 Soluble Factors**

Soluble factors will be analyzed similarly to flow cytometry variables. Cytokines including but not limited to IL-2Ra and IP-10 will be summarized by time point.

### **7.8.3 Gene expression profiling**

Differences in genomic expression patterns in tumor and peripheral blood sample may be summarized for genes of particular interest.

### **7.8.4 Tumor mutation burden**

Potential association between pre-treatment tumor mutation burden and clinical outcomes may be explored.

### **7.8.5 Tumor Biopsy Immunohistochemistry (IHC)**

For association between efficacy and IHC assessment of T-cell infiltration or expression of markers such as MHC I, MHC II, CD3 and CD8 (IHC marker), the below analyses are expected to be performed:

Figures:

- Scatter plot of intensity of IHC markers with clinical outcome annotated (ORR)
- Change of intensity of IHC markers from pre-treatment to on-treatment when available, with clinical outcome annotated (ORR)

#### **7.8.5.1 PD-L1 and Lag-3 Expression**

Analyses of PD-L1 and LAG-3 expression (PDL-1/LAG-3) are descriptive in nature and intended to examine the distribution of PD-L1 and/or LAG-3 expression and assess potential associations between PD- L1/LAG- 3 expression and efficacy measures. If there is an indication of a meaningful association, future work will evaluate PD- L1/LAG- 3 expression as a predictive biomarker, including selection of an optimal PD- L1/LAG- 3 expression cut-off to classify subjects as PD- L1/LAG- 3 positive or PD- L1/LAG- 3 negative.

PD-L1/LAG-3 expression in this section will be defined based on the validated immunoassay method for PD- L1/LAG- 3 IHC assays. PD- L1/LAG- 3 status is a categorical variable by X% cut off for quantifiable PD-L1/LAG-3 expression:

- Positive:  $\geq X\%$  PD- L1/LAG-3 expression
- Negative:  $< X\%$  PD- L1/LAG-3 expression

where X denotes the possible PD- L1 expression levels 1%, 5% and 10% cutoff levels and LAG-3 expression cut-off values of 1%, 5%. Additional cut off values may also be explored, but the 1% cutoff for PD- L1/LAG- 3 will be considered primary.

Analyses of PD- L1/LAG- 3 will include:

- Examine the distribution of PD- L1/LAG-3 expression
- Assess potential association between PD- L1/LAG-3 status and efficacy measures
- Evaluate the potential predictive relationship of the PD- L1/LAG- 3 status and efficacy measures
- Test performance statistics such as sensitivity, specificity, positive predictive value (PPV) and negative predictive value (NPV)
- Assess potential association between PD- L1/LAG-3 status and overall AEs

#### **7.8.5.2 Analyses**

- Descriptive statistics of PD- L1/LAG-3 expression and PD- L1/LAG-3 status, analyses will be based on all evaluable PD-L1/LAG-3 subjects if not otherwise specified:
- Listing of all PD-L1/LAG-3 IHC data.
- Summary of tumor specimen acquisition and characteristics, all randomized subjects.
- Summary statistics of PD-L1/LAG-3 expression by treatment groups of select subgroups and overall.
- Box plot of PD-L1/LAG-3 expression by treatment group and overall.
- Cumulative distribution plot of PD-L1/LAG-3 expression versus population percentile by treatment group and overall.
- Waterfall plots of individual PD-L1/LAG-3 expression by treatment group and overall.

Note: Selected subgroups are identical to the subgroups used for PFS subgroup analysis (Section 7.5.1)

Evaluation of associations between PD-L1/LAG-3 status and efficacy measures. Each analysis will be performed for the subgroups listed below if not otherwise specified:

- Each PD-L1/LAG-3 status and combination thereof subgroup Analyses for PFS endpoint:

For each of the subgroups:

- PFS curves for each treatment group will be estimated using the Kaplan- Meier product limit method. Two-sided, 95% confidence intervals for median PFS will be constructed based on a log-log transformed CI for the survivor function  $S(t)$ .
- Forest plot of Hazard Ratios with 95% CIs

Analyses for OS endpoint:

For each of the subgroups:

- OS curves for each treatment group will be estimated using the Kaplan-Meier product limit method. Two-sided, 95% confidence intervals for median OS will be constructed based on a log-log transformed CI for the survivor function  $S(t)$ .
- Forest plot of Hazard Ratios with 95% CIs
- Analyses for ORR (BOR)
- Box plots of PD-L1/LAG-3 expression versus Response Status by treatment group

For each of the subgroups:

- Frequency and percentage of BOR will be summarized for each treatment group.
- ORR will be computed by treatment group along with exact 95% CIs using the Clopper-Pearson method.

Analyses DOR:

For each subgroup duration of response (DOR) will be summarized by treatment group.

Evaluation of the potential predictive relationship of PD-L1/LAG-3 status for efficacy measures all PD-L1/LAG-3 evaluable subjects

Analyses for PFS endpoint:

A Cox proportional hazards regression model will be fitted for PFS with treatment, PD-L1 status, LAG-3 status, PD-L1\*LAG-3 status, and treatment by PD-L1/LAG-3 status interaction. Although the study is not designed to have substantial power to formally test the interaction of the model, an interaction test at significance level of 0.2 will warrant further exploration and the following statistics will be reported:

- Interaction p-value
- Hazard ratio of treatment vs. control and its associated 95% CI for each of the PD-L1/LAG-3 status subgroup

- Hazard ratio PD-L1/LAG-3 positive vs. negative and its associated 95% CI within each treatment group. For the combination of the two biomarkers, we will designate one of the four cells to be the reference group(the PD-L1-/LAG-3-) and report the ratio of the hazard ratios

Analyses for OS endpoint:

A Cox proportional hazards regression model will be fitted for OS with treatment, PD- L1 status, LAG-3 status, PD-L1\*LAG-3 status, and treatment by PD-L1/LAG-3 status interaction. Although the study is not designed to have substantial power to formally test the interaction of the model, an interaction test at significance level of 0.2 will warrant further exploration and the following statistics will be reported:

- Interaction p-value
- Hazard ratio of treatment vs. control and its associated 95% CI for each of the

PD- L1 status subgroup

- Hazard ratio PD-L1/LAG-3 positive vs. negative and its associated 95% CI within each treatment group. For the combination of the two biomarkers, we will designate one of the four cells (the PD-L1-/LAG-3-) to be the reference group and report the ratio of the hazard ratios.

Analyses for ORR endpoint:

A logistic regression model will be fitted for response (yes=CR or PR, No=SD or PD or unknown) with treatment, PD-L1/LAG-3 status and the treatment by PD-L1/LAG-3 status interaction. Although the study is not designed to have appropriate power to formally test the interaction of the model, an interaction test at significance level of 0.2 will warrant further exploration and the following statistics will be reported:

- Interaction p-value
- Odds ratio of treatment vs. control and its associated 95% CI will be reported for each of the PD-L1/LAG-3 status subgroup
- Odds ratio of PD-L1/LAG-3 positive vs. negative and its associated 95% CI will be reported for each treatment group. For the combination of the two biomarkers, we will designate one of the four cells (the PD-L1-/LAG-3-) to be the reference group and report the ratio of the odds ratio.

Test performance statistics for PD-L1/LAG-3 status vs. efficacy measures on all PD- L1/LAG-3 evaluable subjects:

For each treatment group the following will be produced:

- Contingency table of PD-L1/LAG-3 status by response status (yes=CR or PR; No=SD or PD or unknown).
- Sensitivity, specificity, PPV and NPV will be reported along with the contingency table.

Association of all select AE and PD-L1/LAG-3 expression, all PD-L1/LAG-3 treated subjects  
Overall summary of any select AEs by worst CTC grade (any grade, grade 3-4, grade 5)  
presented by SOC/PT by treatment group for following subgroups will be provided for each PD-  
L1/LAG-3 status subgroup.

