5.4.3 Rationale for Stratification by M-Staging, BRAF, LAG-3, and PD-L1

In order to minimize the potential for imbalances across treatment arms, there will be four stratification factors utilized in this trial: AJCC M stage (M0/M1any[0] versus M1any[1]), BRAF mutation (mutation positive versus wild type), LAG-3 status ($\geq 1\%$ expression versus $< 1\%$ expression) and PD-L1 expression ($\geq 1\%$ tumor cell surface expression versus $< 1\%$ tumor cell surface expression). Prognostic implications of M staging are well established.¹⁹ BRAF mutations have likewise been associated with adverse clinical outcomes in melanoma patients.²⁰ Preliminary data from the CA224020 study have shown that LAG-3 expression may be a strong predictor of efficacy in tumors that have become resistant to anti-PD-1 therapy.²¹ With regard to PD-L1 expression, previous clinical studies with nivolumab monotherapy have shown patients with PD-L1 positive tumors may have higher response rates than those with indeterminate expression.²² Participants in the current trial will therefore be stratified by PD-L1 status as the effect of PD-L1 expression on response to PD-1 and anti-LAG-3 combination therapies is not yet known.

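### The within-arm PD-L1/LAG-3 positive-versus-negative hazard and odds ratios are non-randomized contrasts with no adjustment for M stage, BRAF or other named prognostic factors, so an imbalance in prognosis can bias them

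*SAP*

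**What the plan says.** SAP 7.8.5.2 sets out three models for the relationship between biomarker status and efficacy.

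- **PFS:** "A Cox proportional hazards regression model will be fitted for PFS with treatment, PD-L1 status, LAG-3 status", followed by the product of the two biomarkers and a treatment-by-biomarker interaction.
- **OS:** "A Cox proportional hazards regression model will be fitted for OS with treatment" and the same remaining terms.
- **Response:** "A logistic regression model will be fitted for response" "with treatment, PD-L1/LAG-3 status and the treatment by PD-L1/LAG-3 status interaction".

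The outputs are the interaction p-value, the treatment effect in each biomarker subgroup and, for PFS and OS, "Hazard ratio PD-L1/LAG-3 positive vs. negative and its associated 95% CI within each treatment group". For response the matching output is: "Odds ratio of PD-L1/LAG-3 positive vs. negative and its associated 95% CI will be reported for each treatment group". For the combined biomarkers, ratios of hazard or odds ratios are reported with the double-negative cell as reference. On the interaction, the SAP says only that "an interaction test at significance level of 0.2 will warrant further exploration".

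The documents identify prognostic factors elsewhere. Protocol 5.4.3 states: "Prognostic implications of M staging are well established". It also links BRAF mutation to worse outcomes. SAP 7.5.2 lists age, sex, ECOG status, history of brain metastases and LDH as factors to adjust for when estimating the treatment effect on PFS.

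**The concern.** Randomization makes the two arms comparable. It does nothing to make biomarker-positive and biomarker-negative participants comparable within an arm. If, say, elevated-LDH M stage is less common among LAG-3-positive participants, they will tend to progress later whether or not LAG-3 matters, and the reported ratio will carry that difference. The plan adjusts for prognostic factors in a PFS sensitivity analysis of the treatment effect, which is protected by randomization, and does not adjust the contrast that lacks that protection.

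What is at stake is the reading of LAG-3 and PD-L1 as markers of outcome. SAP 7.8.5.1 makes an indication of a meaningful association the trigger for later work, including the choice of cut-offs.

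**Working it through.** **1. Are the factors really absent?** No plan figure needs reproducing here; this is a textual check.

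- The three models in SAP 7.8.5.2 name no strata and no covariates beyond treatment and the biomarkers.
- The default strata in SAP 7.5 apply only where an analysis is specified as stratified. These are not.
- SAP 7.5.2 includes one PFS Cox model with PD-L1, LAG-3, BRAF and M stage together as covariates, but only its treatment hazard ratio is to be presented.

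So no planned analysis gives an adjusted positive-versus-negative ratio.

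**2. How large could the bias be?** The documents do not report M stage or BRAF by biomarker status, so every input here is assumed. Let *g* be the hazard ratio of one omitted factor, and *p1* and *p0* its prevalence in biomarker-positive and biomarker-negative participants. With a true biomarker hazard ratio of 1.0, the unadjusted ratio is approximately

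(1 + (g − 1)·p1) / (1 + (g − 1)·p0).

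As a check, Cox models were fitted with and without the factor to one simulated data set per row (8,000 participants, 40% biomarker-positive).

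| g | p1 vs p0 | Formula | Simulated, unadjusted | Simulated, adjusted |
|---|---|---|---|---|
| 1.5 | 35% vs 35% | 1.00 | 1.004 | 1.003 |
| 1.5 | 30% vs 40% | 1.15/1.20 = 0.958 | 0.977 | 1.022 |
| 1.5 | 25% vs 45% | 1.125/1.225 = 0.918 | 0.913 | 0.984 |
| 2.0 | 35% vs 35% | 1.00 | 0.986 | 0.980 |
| 2.0 | 30% vs 40% | 1.30/1.40 = 0.929 | 0.961 | 1.026 |
| 2.0 | 25% vs 45% | 1.25/1.45 = 0.862 | 0.897 | 1.014 |

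Each simulated pair shares sampling noise, so unadjusted divided by adjusted is the fairer comparison with the formula. In the four unequal rows it gives 0.977/1.022 = 0.956, 0.913/0.984 = 0.928, 0.961/1.026 = 0.937 and 0.897/1.014 = 0.885. The direction agrees throughout. The formula somewhat overstates the bias at *g* = 2 with a 20-point difference.

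**3. How does this compare with sampling error?** The final PFS analysis has 365 events, or about 182.5 per arm. With 40% positive, the standard error of a within-arm log hazard ratio is about 1/√(182.5 × 0.4 × 0.6) = 0.151. A ratio estimated at 1.0 would have a 95% interval of about exp(±1.96 × 0.151), or 0.74 to 1.34. The log biases run from ln 0.958 = −0.043 to ln 0.862 = −0.148, which is about 0.3 to 1.0 standard errors.

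**4. Which outputs are exposed?** A factor that affects only prognosis has the same distribution in both randomized arms of a biomarker subgroup, so it cancels from a comparison of treatment effects. In simulated trials of 700 participants and 365 events (65% positive, 5- to 20-point imbalance, factor hazard ratio 1.6 or 2.2), the ratio of treatment hazard ratios averaged 0.985 to 1.011, with a Monte Carlo standard error of about 0.012. That held even where the positive-versus-negative hazard ratio averaged 0.86.

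**The case against.** The strongest reply is that these are exploratory summaries and the SAP says so. SAP 7.8.5.1 calls them descriptive and leaves predictive evaluation to future work, and 7.8 allows further methods. The same section plans biomarker expression summaries across the PFS subgroups, which include M stage, BRAF, LDH, brain metastases and ECOG status, so a reader could see whether an imbalance exists. An unadjusted association is also a legitimate quantity, and it matches the unadjusted sensitivity, specificity and predictive values planned alongside it. Finally, PFS was tested on 09MAR2021 and treatment assignments were then unblinded (SAP 5.2.1), so replacing the model now would be a post-unblinding change.

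Most of this stands, and it sets the severity. It does not remove the point. A table that reveals an imbalance does not correct the ratio. Covariates chosen after review of the data are weaker than covariates named beforehand. Reporting adjusted ratios beside the written ones keeps the marginal association and replaces nothing.

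A reader might go further and infer that the evidence on who benefits from relatlimab is confounded too. The documents do not support that. The subgroup treatment effects and the interaction test compare randomized arms. So do the ratios of hazard ratios, if read as ratios of treatment effects, which is their natural meaning.

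**Conclusion.** The point holds in a limited form. The positive-versus-negative ratios for PFS, OS and response are non-randomized and unadjusted, although the documents name relevant prognostic factors that the trial already collects. Under the assumed 10- to 20-point imbalances and a factor hazard ratio of 1.5 to 2, a null hazard ratio would read about 0.86 to 0.96. That is at most about one standard error of a within-arm estimate at 365 events.

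It would be wrong to conclude that these ratios *are* confounded. The documents show no imbalance by biomarker status, and with none there is no bias. The primary PFS test and the OS and ORR tests are untouched. Severity is minor, because only exploratory analyses are involved.

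**What to change.** In SAP 7.8.5.2:

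- Keep the three written models and label their positive-versus-negative ratios *unadjusted association*.
- Add the same ratios from PFS and OS Cox models stratified by BRAF status and AJCC M stage (2 × 2 = 4 strata), and from the ORR logistic model with both as covariates. Take M stage from the clinical database, because SAP 6.2.1 reports that sites did not include LDH values in their M-stage classification at stratification.
- Include age, sex, ECOG status and history of brain metastases from SAP 7.5.2. Do not enter LDH separately: the M-stage factor already carries it (Protocol Appendix 7).
- Date the addition as made after the PFS unblinding.

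The cost is a short SAP addition and a few extra exploratory model runs. No new data are needed, and no alpha or formal test changes.

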## **7.9 Outcomes Research Analyses**

### **7.9.1 EuroQol EQ-5D-3L**

Unless otherwise specified, the analysis of EQ-5D will be performed in all randomized subjects who have an assessment at baseline and at least one or more post-baseline assessments. EQ-5D utility index values will be computed using a scoring algorithm based on the UK MVH-A1 TTO value set. The following descriptive analyses will be conducted.

- EQ-5D questionnaire completion rate, defined as the proportion of questionnaires actually received out of the expected number (i.e., number of subjects on treatment or in follow up), will be calculated and summarized for each assessment time point by treatment group.
- A by-subject listing of EQ-5D with the problem levels for each of the 5 dimensions (mobility, selfcare, usual activities, pain/discomfort and anxiety/depression), health state (5 dimensions digits combined in a 5-digit number) and EQ-VAS will be provided.
- Proportion of subjects reporting problems for the 5 EQ-5D dimensions at each assessment timepoint will be summarized by level of problem and by treatment group. Percentages will be based on number subjects assessed at assessment time point.
- For the EQ-5D Index and visual analog scale (VAS), separately:
  - Mean score and mean change from baseline at each assessment time point will be summarized by treatment group using descriptive statistics (N, mean, SD and 95% CI, median, 25th and 75th percentiles, minimum, maximum).
  - A plot summarizing the mean change from baseline will be presented.

### **7.9.2 FACT-M**

Unless otherwise specified, the analysis of FACT-M will be performed in all randomized subjects who have an assessment at baseline and at least one or more post-baseline assessments. The following descriptive analyses will be conducted.

- FACT-M questionnaire completion rate, defined as the proportion of questionnaires actually received out of the expected number (i.e., number of subjects on treatment or in follow up), will be calculated and summarized for each assessment time point by treatment group.
- For the total score, subscales and GP5, separately:
  - Mean score and mean change from baseline at each assessment time point will be summarized by treatment group using descriptive statistics (N, mean, SD and 95% CI, median, 25th and 75th percentiles, minimum, maximum).
  - A plot summarizing the mean change from baseline will be presented.

- For GP5 only: Number and proportion of subjects endorsing each response option at each assessment timepoint. Percentages will be based on number of subjects assessed at assessment time point.

### **7.9.3 Time to Meaningful Symptomatic Deterioration of FACT-M MS**

The time to meaningful symptomatic deterioration is defined as the time (in months) between the date of randomization and the first date of a 3-point or more decrease from baseline in FACT-M Melanoma Subscale (MS). The focus of this analysis is the period while patients remain on treatment; subjects who did not meet the criteria of a 3-point or more increase from baseline in FACT-M MS will be censored on the date of their last FACT-M assessment. Patients without any PRO measurement are censored at randomization.

Time to meaningful symptomatic deterioration will be analyzed using a Cox proportional hazards model with baseline as a covariate. The estimate of the hazard ratio along with a two-sided 95% CI for the hazard ratio will be calculated.

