Laboratory Tests	X		For Follow-Up Visit 1, onsite/local including Hematology, Serum Chemistry, and Urinalysis as outlined in Table 9.4.4-1 . Repeat at Follow-Up Visit 2 if study treatment related toxicity persists.
Pregnancy Test (WOCBP only)	X		Pregnancy testing is only required at FU Visits 1 and 2 unless increased frequency and duration is required per local regulations.
Efficacy Assessments			
Body Imaging	X	X	Only for participants without BICR-confirmed progression on study therapy. Tumor assessments subsequent to the first assessment should occur every 8 weeks (± 1 week) up to Week 52 and then every 12 weeks (± 1 week) until disease progression is documented or study treatment is discontinued, whichever occurs later Contrast enhanced CT chest, CT (or MRI with and without contrast) abdomen, pelvis, and all known sites of disease. Use same imaging method as was used at screening/baseline. See Section 9.1 .

Table 2-3: Follow-Up Procedural Outline (CA224047)

Procedure	Follow-Up ^a Visits 1 and 2	Survival Follow-Up Visits ^b	Notes
Brain Imaging	X	X	Only for participants without BICR-confirmed progression on study therapy. Participants with a history of brain metastasis or symptoms should have surveillance MRIs per standard of care (approximately every 12 weeks) or sooner if clinically indicated. CT of the brain without and with contrast can be performed if MRI is contraindicated. See Section 9.1 . See Table 9.1.2-1 for instructions on performance of scans in participants with contrast allergies.
PFS2 Assessment	X	X	Following first progression, participants will continue to be followed during the safety and survival Follow-Up Visits. Time of second progression per investigator's assessment will be documented.
Pharmacokinetic (PK) Assessments			
PK and Immunogenicity blood sample	X		Refer to Table 9.5.1-1 for details regarding specific sample timing.
Outcomes Research Assessments			
EQ-5D-3L	X	X	For survival visits, questionnaire can be administered by phone. Pediatric participants (≥ 12 and < 18 years of age) should only complete the EQ-5D-3L and not the WPAI:GH or FACT-M assessments
FACT-M	X		
FACT-M melanoma subscale (MS)		X	For survival visits, MS questionnaire can be administered by phone.
WPAI:GH	X		
Health Care Utilization	X		Health care resource utilization data will be collected by study site staff using the CRF.

Table 2-3: Follow-Up Procedural Outline (CA224047)

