9.1.3 Patient-Reported Outcomes

The evaluation of patient-reported outcomes is an increasingly important aspect of clinical efficacy in oncology trials. Such data provide an understanding of the impact of treatment from the participant's perspective and offer insights into patient experience that may not be captured through physician reporting. Additionally, generic health-related quality of life measures provide data needed for calculating utility values to inform health economic models.

Participants will be asked to complete the Functional Assessment of Cancer Therapy-Melanoma (FACT-M), 3-level version of the EuroQol Group's EQ-5D (EQ-5D-3L), and Work Productivity and Activity Impairment: General Health (WPAI:GH) questionnaires after randomization but prior to first dose, at on-study clinic visits while on treatment, and at Follow-Up Visits 1 and 2. Whereas

all participants will complete the EQ-5D-3L, only those ≥ 18 years of age at baseline will be asked to complete the FACT-M and WPAI:GH. All questionnaires will be provided in the participant's preferred language when available.

In addition, the EQ-5D-3L and the 16-items comprising the Melanoma Subscale (MS) of the FACT-M will be administered by telephone at designated time points during the survival follow-up phase. There exist standardized guides that can be used to facilitate telephone administration of the EQ-5D-3L though a similar guide does not exist for the MS. Participants will be provided with a hard copy of the latter questionnaire to take home and use as a visual aid during telephone interviews.

If exceptional circumstances preclude the continued administration of measures using planned modalities, then alternate administration methods may be required. [Table 2-2](#) and [Table 2-3](#) provide information regarding the timing of patient-reported outcomes assessments.

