10.2.4.3 Outcomes Research

Analyses of EQ-5D-3L, FACT-M (and GP5 item alone), and WPAI:GH scores will be performed in all randomized participants who have an assessment at baseline (Day 1, assessment prior to administration of drug on day of first dose) and at least 1 subsequent assessment while on treatment. Questionnaire completion rate, defined as the proportion of questionnaires actually received out of the expected number, will be calculated and summarized at each assessment point.

EQ-5D-3L data collected during on-study clinic visits, at Follow-up Visits 1 and 2, and during the survival follow-up phase, will be described by treatment group as randomized in the following ways:

- EQ-5D-3L index scores and post-baseline changes in scores will be summarized at each assessment time point using descriptive statistics (ie, N, mean with SD and 95% CI, median, first and third quartiles, minimum, maximum). In the base case, scores will be calculated using the UK preference-weighting algorithm.
- EQ-5D-3L VAS scores and post-baseline changes in scores will be summarized at each assessment time point using descriptive statistics (ie, N, mean with SD and 95% CI, median, first and third quartiles, minimum, maximum).
- The proportion (N) of participants reporting no, moderate, or extreme problems will be presented for each of the 5 EQ-5D-3L dimensions at each assessment time point.
- A by-participant listing of the level of problems in each dimension, corresponding EQ-5D-3L health state (ie, 5-digit vector), EQ-5D-3L index score, and EQ-5D-3L VAS score will be provided.

FACT-M data collected during on-study clinic visits, at Follow-up Visits 1 and 2, and during the survival follow-up phase will be described by treatment group as randomized in the following ways:

- Scores and post-baseline changes in scores for the FACT-M total scale and subscales, and the GP5 will be summarized at each assessment time point using descriptive statistics (ie, N, mean with SD and 95% CI, median, first and third quartiles, minimum, maximum, and frequency of responses for GP5 item).
- The proportion (N) of participants with symptomatic deterioration, defined as a clinically meaningful decline in FACT-M MS score (worsening from baseline ≥ 34 points) or death, will be summarized at each assessment time point (on-study visits only).

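### SAP 7.9.3 states an on-treatment focus for time to symptomatic deterioration, but neither its event clause nor its censoring clause applies that window

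*SAP*

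**What the plan says.** SAP 7.9.3 times the endpoint from randomization to "the first date of a 3-point or more decrease from baseline in FACT-M Melanoma Subscale (MS"). It then says "The focus of this analysis is the period while patients remain on treatment". The censoring rule, in the same sentence, is addressed to "subjects who did not meet the criteria of a 3-point or more increase from baseline in FACT-M MS". Under that rule such participants "will be censored on the date of their last FACT-M assessment". The analysis is a Cox model with baseline as a covariate, reported as a hazard ratio with a 95% CI.

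Protocol 9.1.3 schedules the full FACT-M after randomization but before the first dose, "at on-study clinic visits while on treatment, and at Follow-Up Visits 1 and 2". It adds that the MS items "will be administered by telephone at designated time points during the survival follow-up phase". Protocol Table 2-3 puts the FACT-M and the MS on separate rows, with only the MS at survival visits: "For survival visits, MS questionnaire can be administered by phone". Its footnotes place Follow-Up Visit 1 at 30 days after the last dose (or at discontinuation, if that is more than 42 days after the last dose), Visit 2 at 100 days, and survival visits every 3 months after that.

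Protocol 10.2.4.3 plans a related analysis, the proportion with symptomatic deterioration, which "will be summarized at each assessment time point (on-study visits only"). SAP 7.9.3 contains no such limit.

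**The concern.** The stated focus is not turned into a rule. A programmer has an event clause with no end date and a censoring clause that runs to the last questionnaire, while MS scores exist by design for months after treatment stops. The hazard ratio is supposed to compare symptom burden on treatment. If off-treatment scores enter, it also reflects decline after progression and during next-line therapy, and the mix depends on how long each arm stays on treatment. If off-treatment scores are excluded from events but not from censoring, participants accrue follow-up in which they cannot have an event. The text permits either, and nothing in the result would show which was done.

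**Working it through.** No sample size, power or critical value is given for this endpoint, so there is no planned figure to reproduce. The check sets the clauses against the visit schedule and then illustrates the size.

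**1. Ways to program SAP 7.9.3**

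| Option | Events from | Censoring at | Result |
|---|---|---|---|
| 1 | any MS score | last full FACT-M | off-treatment events count; after Follow-Up Visit 2 a fall reported by phone is an event, but a stable score at the same call adds no follow-up |
| 2 | on-treatment MS only | last FACT-M, as written | follow-up after treatment in which no event can count |
| 3 | any MS score | last MS of any kind | clauses agree, but the stated focus is not respected |
| 4 | on-treatment MS only | last on-treatment MS | clauses agree and match the focus, but the censoring clause does not say this |

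Under option 2 the event-free tail reaches Follow-Up Visit 2, about 100 days after the last dose. With the SAP's conversion of 30.4375 days per month, 100 / 30.4375 = 3.3 months. It is longer if MS-only calls count as FACT-M assessments.

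**2. What the documents say about the window**

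- SAP 6.1 defines on-treatment for adverse events, laboratory tests, pulse oximetry and vital signs, with a 30- or 100-day extension. Questionnaires are not listed.
- SAP 7.9.2 counts participants in follow-up in the expected number of FACT-M questionnaires, so follow-up scores will be in the data.
- The protocol's related proportion is limited to on-study visits. It differs from the SAP endpoint in other ways (it adds death and prints a 34-point threshold), so it is a guide to intent rather than a rule for this analysis.
- Table 2-3 separates the FACT-M from the MS, but Protocol 10.2.4.3 describes survival-phase scores as FACT-M data. Whether an MS-only call sets the censoring date is unsettled.

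**3. Share of events off treatment**

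Model 1 has 100,000 participants per setting. Time on treatment follows the plan's nivolumab PFS assumptions (median 6.9 months, 30% durable) and death follows the OS median of 36.9 months. MS is taken every 28 days on treatment, at days 30 and 100 after it, then every 3 months to month 30. Assumed: MS stable on treatment, visit-to-visit SD of 2 to 4 points, post-treatment decline of 0 to 4 points. Off-treatment share of all counted events:

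| SD | Decline 0 | Decline 2 | Decline 4 |
|---|---|---|---|
| 2 | 25.6% | 41.6% | 50.3% |
| 3 | 23.3% | 31.2% | 36.9% |
| 4 | 22.0% | 26.8% | 31.0% |

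Events after Follow-Up Visit 2 are 8-15% of the total.

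**4. Effect on the hazard ratio**

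Model 2 has 8,000 participants per scenario, 27-month accrual and a 34-month cutoff. Assumed: control median treatment of 6 months, on-treatment deterioration hazard of 0.05 per month in both arms, off-treatment hazard 1 to 3 times that, and completion of 90/70/50% on treatment, at follow-up visits and at survival visits. Because the on-treatment hazards are equal, the on-treatment HR should be 1. Monte Carlo error is about 0.04 (1 SE).

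| Duration ratio | Off-treatment multiple | On treatment only (option 4) | All MS (option 3) | Any MS, full-form censoring (option 1) | Events off treatment |
|---|---|---|---|---|---|
| 1.0 | 1 | 0.97 | 1.01 | 0.99 | 51% |
| 1.0 | 2 | 0.96 | 0.98 | 0.97 | 61% |
| 1.0 | 3 | 1.05 | 1.01 | 1.00 | 64% |
| 1.3 | 1 | 1.06 | 1.01 | 0.96 | 49% |
| 1.3 | 2 | 1.02 | 0.96 | 0.96 | 57% |
| 1.3 | 3 | 0.94 | 0.91 | 0.89 | 62% |
| 1.7 | 1 | 1.02 | 1.04 | 0.93 | 45% |
| 1.7 | 2 | 0.98 | 0.93 | 0.88 | 53% |
| 1.7 | 3 | 0.97 | 0.88 | 0.85 | 56% |

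The largest ratio corresponds to the plan's PFS medians, 11.8 / 6.9 = 1.71, if time on treatment follows PFS. Under option 1, 23-53% of event-free participants have later MS scores that the censoring date ignores, a mean loss of 1.8-5.9 months over all event-free participants. Option 2 was not simulated; by reasoning it dilutes the hazard more in the arm that stops treatment sooner, so it would push the HR the other way.

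**The case against.** The best defence is that the focus statement and the censoring rule form one sentence, so both clauses can be read as limited to treatment. The protocol supports that intent: its related proportion uses on-study visits only, and its questionnaire population needs at least one score while on treatment. On that reading there are no off-treatment events and no mismatch. The endpoint is also exploratory and not formally tested.

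Part of this stands. A reader might infer that the SAP counts falls at follow-up visits and phone calls; it does not say so, it only fails to exclude them. A reader might also infer an established mismatch between events and follow-up at survival calls. That requires the censoring clause to mean the full questionnaire only, and Protocol 10.2.4.3 points the other way. At Follow-Up Visits 1 and 2 the full form is given, so literal use of both clauses produces no mismatch there.

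Nor do the documents support saying that late risk sets hold only future events. Participants still on treatment complete the full FACT-M each cycle and stay at risk. In a repeat of Model 1, eventually event-free participants made up about 18-63% of the literal-rule risk set at months 12-24 with SD 2, though only about 1-6% with SD 4. SAP 7.9.3 plans no survival curve for this endpoint, so there is no late curve to call an artefact.

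The off-treatment share also depends on Follow-Up Visit 1, about one cycle after the last dose. Treating it as on treatment cut the share from about 27-54% to 12-33% in that repeat.

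What the defence does not remove is the literal censoring date. The consistent on-treatment reading works only if the analyst overrides it.

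**Conclusion.** The point holds as a conflict between a stated focus and two clauses that do not apply it. Off-treatment decline can enter an on-treatment hazard ratio, or censoring can extend past treatment, depending on how the text is programmed. The phone-call mismatch is conditional on the meaning of FACT-M in the censoring clause.

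The size is illustrative. Across the two models roughly 20-60% of events fall off treatment. With equal treatment duration, all three simulated readings gave an HR of 0.96-1.05. With a 1.7-fold difference the ranges were 0.97-1.02 on treatment only, 0.88-1.04 with all MS scores, and 0.85-0.93 with full-form censoring. These figures rest on assumed variability, decline, hazards and completion rates that the documents do not give, and differences of one or two Monte Carlo standard errors should not be over-read. No alpha, power or primary conclusion is affected.

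Separately, the censoring clause refers to an increase where the event is a decrease. Higher FACT-M scores mean better functioning (SAP 4.3.4.2), so this is a plain error of direction.

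**What to change.** In SAP 7.9.3, state one window and use it in both clauses. The event is the first MS decrease of 3 points or more at an assessment inside the on-treatment window; event-free participants are censored at their last MS assessment inside that window. In the same edit:

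- say whether Follow-Up Visit 1 is inside the window. Protocol Table 2-2 has no separate end-of-treatment questionnaire visit, so excluding Visit 1 can lose the first score after the final cycle;
- say whether MS-only survival calls count as FACT-M assessments;
- change increase to decrease in the censoring clause.

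If follow-up data are of interest, add a sensitivity analysis that uses every MS assessment for both events and censoring.

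The cost is a few lines of SAP text and a date filter, with fewer events in an exploratory endpoint. No new data are needed.
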